We hypothesize that preterm infants supplemented with early physiologic doses of L-carnitine while on parenteral nutrition will have improved short-term growth parameters and significantly higher neurobehavioral scores when compared with control infants.

Primary Aims:

To determine whether carnitine supplementation is associated with:

- 1. Decreased percent weight loss within the first two weeks of life and decreased length of time to regain birthweight.
- 2. Improved performance on the NICU Network Neurobehavioral Scale (NNNS) at 40 weeks postmenstrual age (+/- 2 weeks).

Secondary Aims:

To determine whether carnitine supplementation is associated with:

- 1. Increased rate of growth of head circumference within the first month of life and increased food efficiency (weight gain/calorie intake) during the supplementation period.
- 2. Normalization of the serum carnitine profile at two weeks of life, compared with infants born at a post-menstrual age 2 weeks later.
- 3. Enhanced brain maturation as measured by amplitude-integrated EEG (aEEG) measurements obtained during the hospital course
- 4. Fewer abnormal findings, better brain growth, white matter development and brain metabolism on brain magnetic resonance imaging (MRI) at 36-40 weeks' corrected age (prior to hospital discharge)

Because of the potential for systemic effects of L-carnitine supplementation, we will also monitor those variables which showed significant difference in our prior study: rates of proven infection, hearing screen failure and PDA ligation.

Primary Outcomes:

- 1. Length of time to regain birthweight,
- 2. Percent weight loss in the first two weeks of life,
- 3. Neurodevelopmental scores on the NICU Network Neurobehavioral Scale (NNNS) at 40 weeks post-menstrual age (+/- 2 weeks)

Methods/Design:

This is a prospective, randomized controlled clinical trial involving infants with gestational age (GA) <32 wks who are born at either the Jack D. Weiler Hospital or the Wakefield Division of Montefiore and admitted to theirNeonatal Intensive Care Unit. Informed consent will be obtained from the parents of eligible patients as early as possible within 72 hours of birth. Infants whose parents have signed an informed consent form will be randomized to receive either carnitine supplementation (50 µmol/kg/day) versus placebo within 72-96 hours of birth.

Inclusion criteria:

- Infants born <32weeks' gestation
- Exclusion criteria:
 - Presence of

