 enrollment and at the end of the intervention (and again if a blood transfusion is administered within this period) 5. Amplitude-integrated EEG readings – within 2-3 of study enrollment and at 28, 32, 36 and 40 weeks' post-menstrual age (dashed lines) 6. Hearing screens – OAE and BAER during the NICU course 7. Brain MRI at 36-40 weeks' GA 8. NNNS at term-equivalent follow-up visit 	3.	(Growth parameters, fluid and nutrition intake and important hospital events), also includes interview with mother to record demographic		96 hours 2 weeks
 study enrollment and at 28, 32, 36 and 40 weeks' post-menstrual age (dashed lines) 6. Hearing screens – OAE and BAER 6. Hearing screens – OAE and BAER 7. Brain MRI at 36-40 weeks' GA 8. NNNS at term-equivalent follow-up visit 	4.	enrollment and at the end of the intervention		28 weeks
during the NICU course 30 week 7. Brain MRI at 36-40 weeks' GA NICU Discharge 8. NNNS at term-equivalent follow-up visit Term-equivalent	5.	study enrollment and at 28, 32, 36 and 40 weeks'		32 weeks
8. NNNS at term-equivalent follow-up visit	6.	• •		36 weeks
	7.	Brain MRI at 36-40 weeks' GA		NICU Discharge
	8.	NNNS at term-equivalent follow-up visit	· ·····	Term- equivalent (due date)
	9.	corrected ago		18-24 months CGA

Serum carnitine profiles: Blood samples (dried blood spots) will be collected at study enrollment and again at two weeks of lifefor measurement of acylcarnitine profiles as well as total and free carnitine levels. Collected samples will be batched and shipped to Baylor College of Medicine. As blood transfusions may impact carnitine levels, these studies will be drawn prior to a blood transfusion required between the first and second weeks of life.

Study specimens will be stored and used for future research purposes provided parents give consent for the storage and future use of the samples. Clinical information will be linked to the study specimens.

Data collection: After study enrollment, medical history and baseline data will be collected for each infant enrolled in the study. Prospective data will be recorded on a weekly basis throughout the NICU stay and after discharge at specific time points. Data will be recorded on standardized case report forms (CRFs) organized into the following categories:

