- 1. Patient demographics: date of birth, birth weight, gestational age as determined by best obstetric estimate or Ballard score, SGA or LGA status, Apgar scores, birth history, delivery room management, gender, ethnicity.
- 2. Maternal characteristics: maternal age, maternal language, ethnicity, presence of prenatal care, type of insurance coverage, maternal educational status, presence of maternal depression, teratogen exposure (alcohol, tobacco or illicit drug use during pregnancy), antenatal steroid use, hypertension/pre-ecclampsia, gestational diabetes/Type I or II diabetes, and maternal infections.
- 3. Management of fluid and nutrition: daily fluid intake and urine output, glucose infusion rate, total caloric intake, total protein intake, and food efficiency (weight gain divided by caloric intake) while on study supplement.
- 4. Hospital course:
 - a. Growth parameters: weight, length and head circumference at birth, daily weight until birthweight regained and then weekly, weekly length, and head circumference two times per week for four weeks)
 - b. Cardiovascular: need for vasopressors, presence of PDA (including medical or surgical treatment; platelet count and mean fluid intake at time of treatment)
 - c. Gastrointestinal: feeding intolerance, NEC, presence of gastrointestinal reflux,
 - Neurological: results of aEEG readings, results of head ultrasounds including presence of germinal matrix/intraventricular hemorrhage and periventricular leukomalacia, cranial MRI results
 - e. Opthalmological: grade of retinopathy of prematurity and treatment or ophthalmologic diagnosis,
 - f. Hematologic: transfusion history including dates
 - g. Infectious disease: presence of concurrent presumed and proven infection,
 - h. Other: performance of any surgical procedures, duration of intravenous access, use of medications, and hearing screen results (OAE and/or ABR) with observed thresholds of hearing frequencies.
 - i. Clinical Risk Index for Babies (CRIB) scores will be calculated for each infant.
 - j. We will also monitor for possible short-term side effects.
- 5. Discharge information: weight, length, head circumference, and diagnoses at time of discharge, routinely-ordered discharge brain MRI findings
- 6. Neurodevelopmental assessment:

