There is a theoretical risk of reduced closure of patent ductus arteriosus (PDA) in infants treated with indomethacin who receive carnitine supplementation as opposed to placebo.²⁸ In our previous study, an increase in PDA ligation among infants treated with indomethacin was seen. The observation may have been due to chance. It is also possible that an interaction between carnitine and indomethacin occurred. Indomethacin enhances the process of apoptosis, which mediates PDA closure.⁵³ Carnitine has been shown to reduce apoptosis in such models as ischemia-reperfusion injury.⁵⁴ However, it should also be noted that the group of carnitine-supplemented infants with the increased rate of PDA ligation had lower birthweight and had received more fluids prior to intervention, compared to the infants in the placebo group. Increased fluid intake has been shown to be associated with failure of medical management of PDA.⁵⁵If this effect was in fact associated with decreased apoptosis, it reinforces our hypothesis regarding neuronal protection, a benefit we feel outweighs a theoretical risk of reduced PDA closure.

Despite this incidental finding, there have been no other reports of adverse effects in neonates receiving supplementation doses (approximately 50 µmol/kg/day) although approximately one-third of NICU's in the United States supplement carnitine routinely in parenteral nutrition. In addition, there have been at least 13 clinical trials of carnitine in premature infants which did not report side effects.

We have established a Data and Safety Monitoring Board. The DSMB will meet approximately every 6 months to review safety data. Meetings will be convened via conference calls. Emergency meetings may be convened at any time by the board in the event that questions/concerns regarding patient safety have been raised or if an unexpected AE/SAE occurs that is possibly related to the study. A report will be circulated to the board members approximately 2 weeks before the board meeting in order to provide them with adequate time to review the materials.

Infants in our study will be monitored closely in order to detect unforeseen side effects. All AEs will be collected and recorded as part of the study. For each, the PI will include the following assessments:

- Anticipated/unanticipated
- Relationship to the study intervention
- Outcome

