The DSMB will review all adverse events as described in the Charter. All unanticipated problems will be reported to the DSMB and IRB within 5 days of the PI becoming aware of the problems.

With the upcoming revisions in the IRB AE reporting policy, we have decided to not follow the current IRB adverse event reporting policy dated 2008; instead we will report AEs to the IRB as follows:

- 1. Unanticipated Problems defined as anyevent, deviation, or problem
 - thatmeetsallofthefollowingcriteria:
 - unanticipated; AND
 - possibly,probablyordefinitelyrelatedto studyparticipation;AND
 - fatal,life-threatening,orseriousORsuggestsgreaterriskofharmtostudy participant(s)or othersthanwaspreviouslyknownorrecognized
- 2. Deathofaparticipantifitoccurswithin30 daysofadministrationofthestudymedication
- 3. AProtocolDeviation or an incident, experience,oroutcomethatmayplacetheparticipantorothersatgreatermedical, physiological,socialriskoreconomicriskthanwaspreviouslyknownorrecognized
- 4. AnydeviationfromIRBorInstitutionalPolicyorProcedurewhichhasthepotentialto adverselyimpactoneormoresubjectsortheoverallintegrityofdatacollected
- 5. AnyreportingthattheIRBcitesasaconditionofapprovaloftheprotocol
- 6. Complaintfromaparticipantorotherindividualwhenthecomplaintindicates unexpectedrisksorthecomplaintcannotberesolvedbytheresearchteam

- 7. DeviationfromtheIRBInformedConsentPolicy
- 8. Systematicdatacollectionerrors
- 9. Breachofconfidentiality

It is well-known that the very preterm, low birth weight infants included in this study have increased mortality compared to full-term infants. Review of our own Weiler NICU data in 2010 revealed a high mortality rate ininfants less than 30 weeks gestational age: approximately 75% for infants of gestational age of 23 weeks, 24% for gestational age 24-26 weeks, and 5% for infants of gestational age 27 – 29 weeks. Thus, we expect similar rates in infants enrolled in our study.

An additional amount of blood will be drawn as part of the study protocol. The estimated amount of blood is approximately $200 - 300 \mu$ I two to three times over the course of the study. The blood draw will be obtained with other routine bloodwork whenever possible in order to avoid additional discomfort to the infant.

Benefits:

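### The stated risk is reduced ductal closure after indomethacin, but the only PDA outcome named for monitoring is ligation, and the protocol plans no by-arm comparison of closure failure

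*Combined protocol and SAP*

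**What the plan says.** Risks and Discomforts states the harm in terms of closure: "There is a theoretical risk of reduced closure of patent ductus arteriosus (PDA) in infants treated with indomethacin who receive carnitine supplementation", as opposed to placebo. The evidence behind it is a surgical outcome: "In our previous study, an increase in PDA ligation among infants treated with indomethacin was seen". The same section offers three explanations for that finding: chance, an interaction between carnitine and indomethacin acting through apoptosis, and imbalance in birthweight and fluid intake. It then judges that the hoped-for neuronal protection outweighs the closure risk.

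The closing paragraph of Secondary Aims lists what will be monitored for systemic effects: "we will also monitor those variables which showed significant difference in our prior study: rates of proven infection, hearing screen failure and PDA ligation". Ligation is the only PDA variable in that list.

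The Data collection section is wider. Its cardiovascular item (4.b) records "presence of PDA (including medical or surgical treatment; platelet count and mean fluid intake at time of treatment". On timing, it says "Prospective data will be recorded on a weekly basis throughout the NICU stay". Discharge diagnoses are also recorded. All adverse events are collected, and the DSMB reviews them as its Charter describes. Deaths within 30 days of study medication are reported to the IRB.

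Outcome Measures assigns Fisher's exact or chi-square tests to nominal data but does not name PDA among its examples.

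**The concern.** The harm as worded and the variable monitored are not the same thing. Ligation lies downstream of failed closure. It requires that the ductus stays open, that the infant survives long enough, and that the clinical team decides to operate. An infant can have the named harm and add nothing to the numerator of the ligation rate.

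This matters more for PDA than for the other two monitored variables. The background section reports lower rates of infection and hearing screen failure with carnitine in the prior study, whereas PDA ligation was the one difference in the direction of harm. The benefit-risk argument is also made in terms of closure, and the plan defines no outcome that would inform it. If carnitine did reduce closure, the ligation rates could look similar in the two arms while the relevant information sat untabulated on the case report forms.

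**Working it through.** **1. What each source captures.** The documents give no PDA rate, margin or power, so there is no figure of the plan's own to reproduce. The check is a comparison of sections.

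| Infant | Ligation rate (Secondary Aims) | Elsewhere in the protocol |
|---|---|---|
| Ductus ligated | Event | Form item 4.b |
| Ductus treated medically, stays open, no surgery | Non-event | Presence and treatment in item 4.b; response to treatment not explicitly listed |
| Discharged with open ductus | Non-event | Indirectly, through discharge diagnoses |
| Dies before ligation | Non-event | Adverse event and death reporting; ductal status at death not explicitly listed |

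The right-hand column shows partial capture in every row. In the protocol, no row leads to a defined comparison of closure failure by arm, to an indomethacin-treated denominator, or to a rule for death before ligation.

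**2. Deaths.** Risks and Discomforts gives the unit's 2010 mortality as about 75% at 23 weeks, "24% for gestational age 24-26 weeks" and 5% at 27-29 weeks, and expects similar rates in the trial. Per 50 infants of 24-26 weeks, expected deaths are 0.24 × 50 = 12. If none of the 12 had been ligated, all 12 would stay in the denominator as non-events, and the crude ligation rate could not exceed 38/50 = 76%. The documents do not say when deaths occur relative to ligation, so the share that is actually unligated is unknown. Enrolment up to 72 hours, and the exclusion of infants not expected to live 72 hours, would remove some early deaths.

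**3. Does a wider outcome gain sensitivity?** Illustration only: all event rates are assumptions. Power of a two-sided Fisher exact test at 0.05, with 75 per arm (half of the 150 to be recruited):

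| Assumed rates, placebo v carnitine | Power |
|---|---|
| 5% v 10% | 0.13 |
| 10% v 20% | 0.32 |
| 15% v 30% | 0.53 |
| 20% v 40% | 0.71 |

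If ligation is 10% v 20% and all closure failures are 20% v 40%, widening the outcome raises power from 0.32 to 0.71. That assumes the doubling holds in the added events too. If the added events are 10 percentage points in each arm, with no difference between arms, the comparison becomes 20% v 30% and power falls from 0.32 to 0.23.

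The risk concerns only indomethacin-treated infants, whose number is not given. With an assumed 20 such infants per arm, 20% v 40% has power 0.19. The direction and size of any gain therefore depend entirely on assumptions that the documents cannot settle.

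**The case against.** Ligation is a reasoned choice. The stated rule is to monitor what differed in the prior study, and what differed was ligation. Reduced closure is the protocol's theoretical explanation of that signal. Keeping the same variable allows a like-for-like check. This stands, and ligation should stay.

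A reader might infer that ligation is all the trial looks at and that infants with an open ductus, or who die, are counted as safe. The documents do not support that. The form records PDA presence and treatment, all adverse events go to the DSMB, and deaths within 30 days are reported. Such infants are non-events in one rate; nothing classes them as safe. What the DSMB tabulates is left to a Charter that is not available here, so the protocol cannot be said to prove that monitoring misses them.

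A reader might also want a single composite: repeat medical course, ligation, open ductus at discharge, or death with an open ductus. That goes too far on the existing fields, because treatment response, number of courses and ductal status at death or discharge are not explicitly listed. A repeat course also depends on a clinician's decision, as ligation does, and the working shows that a broader outcome can lose power.

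Finally, deaths unrelated to treatment would lower both ligation rates rather than conceal a difference outright. That is fair, and no differential mechanism is shown. It does not remove the need to say how death before ligation is handled. Nor does case-by-case adverse event review replace a defined comparison between arms.

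**Conclusion.** The point holds as a gap in outcome definition. The risk is stated as failed closure, ligation is the only PDA outcome named for monitoring, and the PDA and death data that the trial already gathers are not turned into a by-arm comparison of closure failure. It is a worthwhile, inexpensive improvement to the safety analysis and does not affect the primary outcomes.

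No size of loss is shown. The power figures rest on assumed rates and should not be cited as a demonstrated loss. The 24% mortality figure shows that death before ligation needs a rule at 24-26 weeks; it does not measure how many closure failures would go uncounted. The conclusion is conditional on the DSMB Charter not already specifying these summaries. If it does, the protocol need only say so.

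**What to change.** Keep ligation as the monitored variable, for comparison with the prior study. Add to the safety analysis and the DSMB report, by arm in all randomised infants and each shown separately:

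- (a) PDA present after the start of study supplement;
- (b) medical treatment for PDA;
- (c) ligation;
- (d) ligation or death before ligation.

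Repeat the table descriptively in indomethacin-treated infants. State that treatment may begin after randomisation, so this subgroup is not protected by randomisation and should not carry a formal test.

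If the PDA field on the form is clarified to record ductal status at last assessment, discharge or death, also report persistent PDA after medical treatment.

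The cost is a few more safety tables and, for the last item, a small clarification of an existing form field. The components differ in severity, which is why they should be shown separately and not only combined.

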Study supplementation: Infants randomized to the treatment group will receive 50 µmol/kg/day of Lcarnitine intravenously for 2 weeks, and infants randomized to placebo will received 5% glucose, similar volume to the L-carnitine group. At two weeks, sufficient carnitine is provided in enteral feeds of either breast milk or infant formula. If no intravenous access is available before the supplementation endpoint, the equivalent dose of enteral study supplement (L-carnitine or placebo) will be administered.⁴¹ Parenteral and enteral nutrition will be provided according to standard NICU protocol.

Of note, as many as 10% of the infants in the study will likely continue to rely primarily on parenteral nutrition beyond the proposed two-week supplementation period. Enteral feeds may be withheld from these infants due to underlying illnesses such as sepsis or gastrointestinal disorders like necrotizing enterocolitis. Due to the presence of underlying illness, these infants are at an even higher risk for developing developmental delays.⁴²Therefore, in study patients who are not receiving adequate enteral nutrition (100 cc/kg/day of enteral intake) after 2-weeks of study supplements, carnitine supplementation will be continued until these infant are receiving adequate enteral feeds; at this point, their physiologic carnitine requirements will be met by enteral nutrition alone.

Timeline of Assessments:

- a. Within 72 hours of birth
 - i. Patient enrollment and initiation of study protocol

- ii. Initial carnitine panel drawn
- iii. Initial aEEG reading obtained within 2-3 days of study initiation
- iv. Study Supplement begins within 72-96 hours of birth
- b. Two weeks after study initiation
 - i. Study Supplement concludes (in a small sub-set of patients, study supplementation will be continued until enteral feeds reach 100 cc/kg/day)
 - ii. Follow-up carnitine panel drawn (in addition, as blood transfusions may impact carnitine levels, serum carnitine profiles will be drawn prior to blood transfusion administered between the first and second weeks of life)
- c. aEEG readings will be obtained within 2-3 days of study initiation and at the following post-menstrual ages: 28 weeks (if infant <27 weeks at birth), 32 weeks', 36 weeks', and at 40 weeks' (if infant is still admitted to the NICU).
- d. 36-38 weeks' corrected age
 - i. Cranial MRI
- e. 40 weeks GA (+/- 2weeks)
 - i. Neurodevelopmental assessment

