- f. Neurodevelopmental assessment at 18-24 months corrected age
 - i. Bayley Scales of Infant and Toddler Development III (BSID-III)
 - ii. Modified Checklist for Autism in Toddlers (M-CHAT)
 - iii. Child Behavior Checklist (CBCL)

Individual Infant Timeline:

 2. Study supplement given (within 24 hours of enrollment for total 2 weeks or until enteral intake is at 100 cc/kg/day) 3. Data collection throughout the NICU course (Growth parameters, fluid and nutrition intake and important hospital events), also includes interview with mother to record demographic information and maternal characteristics 4. Blood carnitine panels – drawn at study enrollment and at the end of the intervention (and again if a blood transfusion is administered within this period) 5. Amplitude-integrated EEG readings – within 2-3 of study enrollment and at 28, 32, 36 and 40 weeks' post-menstrual age (dashed lines) 6. Hearing screens – OAE and BAER during the NICU course 7. Brain MRI at 36-40 weeks' GA 8. NNNS at term-equivalent follow-up visit 	1	Study Enrollment (within 72 hours of birth)	Birth	
 24 hours of enrollment for total 2 weeks or until enteral intake is at 100 cc/kg/day) 3. Data collection throughout the NICU course (Growth parameters, fluid and nutrition intake and important hospital events), also includes interview with mother to record demographic information and maternal characteristics 4. Blood carnitine panels – drawn at study enrollment and at the end of the intervention (and again if a blood transfusion is administered within this period) 5. Amplitude-integrated EEG readings – within 2-3 of study enrollment and at 28, 32, 36 and 40 weeks' post-menstrual age (dashed lines) 6. Hearing screens – OAE and BAER during the NICU course 7. Brain MRI at 36-40 weeks' GA 8. NNNS at term-equivalent follow-up visit 				0 hours
 3. Data collection throughout the NICU course (Growth parameters, fluid and nutrition intake and important hospital events), also includes interview with mother to record demographic information and maternal characteristics 4. Blood carnitine panels – drawn at study enrollment and at the end of the intervention (and again if a blood transfusion is administered within this period) 5. Amplitude-integrated EEG readings – within 2-3 of study enrollment and at 28, 32, 36 and 40 weeks' post-menstrual age (dashed lines) 6. Hearing screens – OAE and BAER	2.	24 hours of enrollment for total 2 weeks		72 hours

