The effect of L-carnitine supplementation on outcome measures in enrolled infants will be examined for significance by comparing the two groups using unpaired data analysis with the assistance of a statistician. Continuous data (percent weight loss, time to regain birthweight, NNNS score, BSID-III scores) will be compared between the "placebo" and the "carnitine supplemented" groups by unpaired student t-test (a 2 tailed P value <0.05 will be considered to indicate statistical significance) or Wilcoxon's rank sum test for non-parametric parameters. Unmatched nominal data will be compared using Fisher's Exact Test or Chi-square test as required (e.g.: presence or absence of normalization of the carnitine profile; or presence or absence of pathological findings on the discharge MRI). Logistic regression models will be used to adjust for potentially confounding factors including gestational age, birth weight, race, gender, Apgar scores.

Risks and Discomforts:

A brief description of the risks and discomforts associated with this study is included in the protocol consent form and will be discussed in detail with each family at the time of study enrollment.

Carnitine is routinely administered with parenteral nutrition in approximately one-third of the neonatal intensive care units in the United States, although not in the Jack D. Weiler Hospital or Montefiore North Division NICU's. Carnitine is FDA-approved, and there have been no reports of severe toxicity from

overdose. Data available from the adult literature reports side effects of mild gastrointestinal symptoms such as gastritis, vomiting, diarrhea or abdominal cramping; body odor; and seizures, in patients with or without a known seizure disorder. These side effects are dose-dependent and might be avoided by slow consumption of the solution or greater dilution. One investigator reported transient elevation of triglycerides and increased platelet aggregation in uremic patients with severe renal insufficiency who received high doses of carnitine supplementation.⁵²

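### Both primary weight outcomes are counted from birth, before dosing starts, and the planned unadjusted test leaves the pre-treatment weights unused: precision is lost, though no bias arises.

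*Combined protocol and SAP*

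**What the plan says.** All references are to the combined protocol and SAP.

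- **Outcome.** Primary Outcomes lists "Percent weight loss in the first two weeks of life" alongside time to regain birthweight. The window opens at birth. The reference weight, and whether the loss is the maximum or the value at a fixed day, are not spelled out.
- **Start of treatment.** Timeline of Assessments: "Study Supplement begins within 72-96 hours of birth". Methods/Design gives the same interval: carnitine "versus placebo within 72-96 hours of birth". The Individual Infant Timeline instead ties the start to enrolment, within "24 hours of enrollment for total 2 weeks". Because consent is sought as early as possible in the first 72 hours, that wording allows some infants to start sooner.
- **Weights recorded.** Data collection, item 4a: "daily weight until birthweight regained and then weekly".
- **Analysis.** Outcome Measures: "Continuous data (percent weight loss, time to regain birthweight, NNNS score, BSID-III scores) will be compared" between arms "by unpaired student t-test", or by a rank-sum test. No covariate is named for this comparison. The only adjustment described is "Logistic regression models will be used to adjust for potentially confounding factors including gestational age, birth weight, race, gender, Apgar scores".

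**The concern.** Part of what the two weight outcomes measure happens before the infant receives anything. That part differs between infants for reasons unrelated to carnitine, so it widens the standard error. It can also differ between arms by chance, and the unadjusted comparison passes such a difference straight into the estimate.

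The plan does not use the information that would deal with this. Logistic regression does not suit a continuous outcome such as percent loss, and its covariate list names birth weight but no later pre-treatment weight. Nothing in the plan resets the baseline or uses the early weight change. Two of the three primary outcomes are affected.

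**Working it through.** **Inputs.** SD 6.2, difference 3.1, 50 per arm, alpha 0.05 and power 0.80 come from Sample size and its table. The two-tailed test comes from Outcome Measures. The start of supplement comes from Timeline of Assessments. The correlation r between pre-treatment percent weight change and the outcome is not in the documents; 0.3, 0.5 and 0.7 are assumptions.

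**1. Untreated part of the window.** 72 to 96 hours is 3 to 4 days: 3/14 = 21% and 4/14 = 29% of the two weeks. Under the Individual Infant Timeline it could be shorter for infants enrolled early.

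**2. The plan's own figure.** Standardised difference d = 3.1/6.2 = 0.5. Noncentrality = d × √(n/2) = 0.5 × √25 = 2.5, with 98 degrees of freedom.
- One-sided alpha 0.05: power 0.799. The stated 0.80 reproduces.
- Two-sided alpha 0.05, the test actually planned: power 0.697.

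**3. Gain from adjustment.** Residual SD = 6.2 × √(1 − r²), so d becomes 0.5/√(1 − r²). Power is two-sided at 50 per arm.

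| r (assumed) | Residual SD | d | Noncentrality (5d) | Power |
|---|---|---|---|---|
| 0 | 6.2 | 0.500 | 2.50 | 0.70 |
| 0.3 | 5.9 | 0.524 | 2.62 | 0.74 |
| 0.5 | 5.4 | 0.577 | 2.89 | 0.82 |
| 0.7 | 4.4 | 0.700 | 3.50 | 0.93 |

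An r of about 0.47 gives two-sided power of 0.80 at 50 per arm (0.45 on the normal approximation). The degrees of freedom used by the covariate and strata change these powers by less than 0.001.

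**4. Chance imbalance.** With 50 per arm, the between-arm difference in pre-treatment change has standard error √(2/50) = 0.2 of its own SD. A difference larger than 0.2 SD in either direction therefore has probability P(|Z| > 1) = 0.32. A 0.2 SD difference moves the unadjusted estimate by r × 6.2 × 0.2 = 0.37, 0.62 or 0.87 points at r = 0.3, 0.5 or 0.7, against a target of 3.1.

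**5. What adjustment does not recover.** Suppose the outcome is maximum loss from birthweight, a share f of infants reach their lowest weight before the first dose, and the effect in the others is 3.1 points. The average effect is then 3.1 × (1 − f): 2.79, 2.48 or 2.17 points for f = 0.1, 0.2 or 0.3, with unadjusted two-sided power of 0.61, 0.51 or 0.41. The share f is an assumption. A covariate reduces residual variance but leaves 3.1 × (1 − f) unchanged.

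**The case against.** The strongest reply is that the planned test is valid. Allocation is randomised and blinded, so pre-dose loss is balanced in expectation and the type I error is unaffected. A reader might infer that the estimate is biased; the documents do not support that. This part of the reply stands, and it makes the point an efficiency improvement rather than an error.

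Four further objections also limit the point:

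- **The gain is unknown.** At r = 0.3 it is only about 4 percentage points of power. Randomization already stratifies on gestational age and small-for-gestational-age status because both affect the outcomes, so part of any correlation may overlap with the strata.
- **The shortfall from 0.80 to 0.70 has another cause.** A reader might blame it on pre-dose weight loss. Step 2 shows that it comes from one-sided versus two-sided alpha. The SD of 6.2 appears to be measured from birth, so the planned power already contains the early variation.
- **Adjustment is not a full cure.** A reader might expect it to remove all pre-dose noise, or to restore an effect in infants whose lowest weight came before dosing. It does neither: at r = 0.7 the residual SD is still 4.4, and step 5 is untouched.
- **The untreated share is not settled.** The 21–29% figure follows Methods/Design and Timeline of Assessments. The Individual Infant Timeline allows earlier starts.

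It could also be said that the covariate list is open and includes birth weight. That list belongs to a logistic model, however, and no passage commits to using an early weight change for a continuous outcome. None of these objections gives a reason to leave the collected weights out of the analysis.

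**Conclusion.** The point holds as a loss of precision and an exposure to chance imbalance in two primary outcomes, correctable at almost no cost. The outcome window, the later start of dosing, the daily weights and the unadjusted comparison are all in the text.

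The size is conditional. Two-sided power rises from 0.70 to 0.74, 0.82 or 0.93 for r = 0.3, 0.5 or 0.7. This assumes SD 6.2, a 3.1-point difference, 50 analysed infants per arm and a linear relation. A positive r is expected because early loss is a component of loss from birth, but its value cannot be taken from the documents. It will be smaller where randomisation comes earlier, since less of the early loss has then occurred. For time to regain birthweight the direction is the same, but the documents give no separate basis for a size.

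**What to change.** 1. **Percent weight loss.** Make the primary analysis a linear model (ANCOVA) with treatment, percent weight change from birth to the last weight at or before randomisation, and the randomisation strata. Taking the covariate at randomisation defines it for every randomised infant, including any never dosed, which suits the intent-to-treat analysis. An infant whose only weight by then is birthweight has a change of zero. State the reference weight and whether the outcome is maximum loss.
2. **Time to regain birthweight.** Use the same covariates in a named model with its effect measure stated in advance, for example a linear model for the difference in mean days if that remains the target. A hazard model would answer a different question, because an adjusted hazard ratio is not the unadjusted one estimated more precisely.
3. **Supportive only.** Loss from the first-dose weight may be reported alongside. It will pile up at zero for infants already gaining weight at first dose.
4. **Reconcile** the statements on when the supplement starts in Methods/Design, Timeline of Assessments and the Individual Infant Timeline.

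The cost is analysis wording, settled before unblinding. The weights are already collected, and sample size and data collection stay as they are. The one-sided versus two-sided power discrepancy needs its own correction.
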